6.3.2 Recommended Dose Modifications for dexamethasone Treatment Associated Toxicity

The primary complications of dexamethasone requiring a dose reduction or discontinuation of therapy will be severe allergic reaction, psychosis, self-reported or diagnosed infection or

hyperglycemia requiring hospitalization. In case of severe allergic reaction or psychosis we will discontinue dexamethasone therapy. Otherwise, dexamethasone will be reduced or discontinued in accordance with clinical guidelines. Re-escalation is allowable.

6.4 Excluded Concomitant Medications and Procedures

The following medications and procedures are prohibited during the study.

Systemic treatment with any of the following metabolizing enzyme inducers should be avoided, unless there is no appropriate alternative medication for the patient's use (Rationale: If there were to be a drug-drug interaction with an inducer, ixazomib exposure would be decreased):

- Strong CYP3A inducers: rifampin, rifapentine, rifabutin, carbamazepine, phenytoin, and phenobarbital

The following medicinal products and procedures are prohibited during the study.

- Excluded dietary supplements include St. John's wort
- Platelet transfusions to help patients meet eligibility criteria are not allowed within 3 days prior to study drug dosing for any dosing day

6.5 Permitted Concomitant Medications and Procedures

The following medications and procedures are permitted during the study:

- Antiemetics, including 5-HT3 serotonin receptor antagonists, may be used at the discretion of the investigator.
- Loperamide or other antidiarrheal should be used for symptomatic diarrhea at discretion of the investigator. The dose and regimen will be according to institutional guidelines. Intravenous fluids should be given to prevent volume depletion.
- Growth factors (eg, granulocyte colony stimulating factor [G-CSF], granulocyte macrophage-colony stimulating factor [GM-CSF], recombinant erythropoietin) are permitted. Their use should follow published guidelines and/or institutional practice; however, alternative usage may be reviewed with the Millennium Clinical or Medical Representative. Erythropoietin will be allowed in this study. Their use should follow published guidelines and/or institutional practice.
- Patients should be transfused with red cells and platelets as clinically indicated and according to institutional guidelines as long as "3 days prior to study drug dosing for any dosing day" – per excluded procedures in section 6.4 above.
- Antiviral therapy such as acyclovir may be administered if medically appropriate.
- Concomitant treatment with bisphosphonates will be permitted, as appropriate.
- Patients who experience worsening neuropathy from baseline may be observed for recovery, and have dose reductions/delays as indicated in the protocol, and any supportive therapy or intervention may be initiated as appropriate at the discretion of the investigator.
- Supportive measures consistent with optimal patient care may be given throughout the study.

6.6 Precautions and Restrictions

Fluid deficit Fluid deficit should be corrected as per standard of care before initiation of treatment and during treatment.

Pregnancy

It is not known what effects ixazomib has on human pregnancy or development of the embryo or fetus. Therefore, female patients participating in this study should avoid becoming pregnant, and male patients should avoid impregnating a female partner. Nonsterilized female patients of reproductive age group and male patients should use effective methods of contraception through defined periods during and after study treatment as specified below.

Female patients must meet 1 of the following:

- Postmenopausal for at least 1 year before the screening visit, or
- Surgically sterile, or
- If they are of childbearing potential, agree to practice 2 effective methods of contraception from the time of signing of the informed consent form through 90 days after the last dose of study drug, or
- Agree to practice true abstinence, when this is in line with the preferred and usual lifestyle of the subject. (Periodic abstinence [eg, calendar, ovulation, symptothermal, postovulation methods] and withdrawal are not acceptable methods of contraception.)

Male patients, even if surgically sterilized (ie, status postvasectomy) must agree to 1 of the following:

- Practice effective barrier contraception during the entire study treatment period and through 90 days after the last dose of study drug, or
- Agree to practice true abstinence, when this is in line with the preferred and usual lifestyle of the subject. (Periodic abstinence [eg, calendar, ovulation, symptothermal, postovulation methods for the female partner] and withdrawal are not acceptable methods of contraception.)

6.7 Preparation, Reconstitution, and Dispensing

Ixazomib is an anticancer drug and as with other potentially toxic compounds caution should be exercised when handling ixazomib capsules.

Dexamethasone is a corticosteroid drug and will be provided by the study sponsor through the UW-Pharmaceutical Research Center (PRC).

Subjects will be dispensed one cycle of ixazomib and dexamethasone at each visit.

Ixazomib: Subjects will be dispensed a wallet/carton of 3 capsules in each wallet/carton.

Dexamethasone: Subjects will be dispensed 15 4mg tablets in an amber bottle per cycle.

6.8 Packaging and Labeling

The study drug ixazomib capsules will be provided by Millennium. The study drug will be labeled and handled as open-label material, and packaging labels will fulfill all requirements specified by governing regulations.

The capsules are individually packaged using cold-form foil-foil blisters that are in a child-resistant carton. There are 3 capsules in each wallet/carton.

Dexamethasone 4mg tablets will be provided by the UW-PRC. For each 20 mg dose, 5 tablets will be prepared in a small package. Three packages of 20 mg total dexamethasone tablets will

be used for each cycle. The PRC will provide treatment for one cycle at a time. The package will be provided to subjects at each study visit.

6.9 Storage, Handling, and Accountability

Upon receipt at the investigative site, ixazomib should remain in the blister and carton provided until use or until drug is dispensed. The container should be stored at the investigative site refrigerated (36°F to 46°F, 2°C to 8°C). Ensure that the drug is used before the retest expiry date provided by Millennium. Expiry extensions will be communicated accordingly with updated documentation to support the extended shelf life.

In countries where local regulations permit, ixazomib capsules dispensed to the patient for take-home dosing should remain in the blister packaging and refrigerated as noted above until the point of use. The investigative site is responsible for providing the medication to the patient in the correct daily dose configurations. Comprehensive instructions should be provided to the patient in order to ensure compliance with dosing procedures. Patients who are receiving take-home medication should be given only 1 cycle of medication at a time. Patients should be instructed to store the medication refrigerated (36°F to 46°F, 2°C to 8°C) for the duration of each cycle. Patients should be instructed to return their empty blister packs to the investigative site, rather than discarding them. Reconciliation will occur accordingly when the patient returns for their next cycle of take-home medication. Any extreme in temperature should be reported as an excursion and should be dealt with on a case-by-case basis.

Ixazomib will be handled with due care. Patients should be instructed not to chew, break, or open capsules. In case of contact with broken capsules, raising dust should be avoided during the clean-up operation. The product may be harmful by inhalation, ingestion, or skin absorption. Gloves and protective clothing should be worn during cleanup and return of broken capsules and powder to minimize skin contact.

The area should be ventilated and the site washed with soap and water after material pick-up is complete. The material should be disposed of as hazardous medical waste in compliance with federal, state, and local regulations.

In case of contact with the powder (eg, from a broken capsule), skin should be washed immediately with soap and copious amounts of water for at least 15 minutes. In case of contact with the eyes, copious amounts of water should be used to flush the eyes for at least 15 minutes. Medical personnel should be notified. Patients are to be instructed on proper storage, accountability, and administration of ixazomib, including that ixazomib is to be taken as intact capsules.

Dexamethasone 4mg tablets will be provided by the UW-PRC. For each 20 mg dose, 5 tablets will be prepared in a small package. Three packages of 20 mg total dexamethasone tablets will be used for each cycle. The PRC will provide treatment for one cycle at a time. The package will be provided to subjects at each study visit.

6.10 Study Drug Compliance

Study drug will be administered or dispensed only to eligible patients by the investigator, identified sub-investigator(s), or study coordinators. The appropriate study personnel will maintain records of study drug receipt and dispensing. The study personnel will monitor the following compliance

criteria quarterly for subjects to remain in the study (i.e. subjects <75% study drug compliance will be re-educated). If they fall below 75% study drug compliance again, they will be withdrawn.

6.11 Treatment Assignment (*if applicable*)

N/A

6.12 Termination of Treatment and/or Study Participation

Patients will be informed that they have the right to withdraw from the study at any time for any reason, without prejudice to their medical care. The investigator also has the right to withdraw patients from the study for any of the following reasons:

- If study drug is discontinued due to AE
- Protocol violation
- Lost to follow-up
- Study terminated
- Non-compliance as defined above in section 6.10

Patients who are withdrawn from the study will not be replaced. The primary reason for patient's withdrawal from the study should be recorded in the source documents and CRF. Subjects will complete an early termination visit.

6.14 Specimen Handling and Confidentiality

Samples that will be sent to the Terasaki Research Foundation Laboratory and University of Michigan will be labeled with the study ID number, date of service and subject age. Researchers at outside institutions will not have access to the key that links the code to identifiable information. Any leftover samples that are not used for the analysis will be destroyed after the study is over. The Terasaki Research Foundation Lab will perform analysis of HLA-DSA, IgG subclasses, ETA-R and AT1-R antibodies in 10 subjects at 5 time points (50 samples total).

6.15 Bone Marrow Studies

Mechanistic studies on B cells and plasma cells (University of Michigan) and mesenchymal stromal cells (UW) will be conducted to better understand the effect of treatment on desensitization. [name] and [name] at UM will participate in the research by processing bone marrow studies (ASCs, BAFF/APRIL). All subjects will be enrolled in the IXADES study at the University of Wisconsin-Madison. University of Michigan will not be involved with subject recruitment or subject interaction. The samples that will be sent to the University of Michigan will be labeled with a study ID number and will contain; date of service, and subject age. [name] and [name] will process the samples in the lab and perform mechanistic studies to achieve the aims of the research. [name] and [name] will analyze the bone marrow samples, provide the results to the study team at UW, and assist with writing the manuscript. [name] and [name] will not have access to the key to the code. The UW study team will communicate with the study team at the University of Michigan once per month through phone calls or e-mails.

A portion of marrow aspirates will be saved at UW for future research studies related to sensitization or transplantation. In addition, the samples may be used in a future therapeutic study to reinject mesenchymal stromal cells in subjects who did not achieve desensitization

through the current study. Samples will be banked at UW for an indefinite period of time. Subjects may withdraw their permission at any time.

7. STATISTICAL AND QUANTITATIVE ANALYSES

7.1 Statistical Methods

More than 50% of patients with CDC T cell crossmatch titers $\geq 1:8$ and/or cPRA $> 80\%$ fail to respond to desensitization (5, 8). In this pilot exploratory, proof of concept, open-label, single-center phase II clinical trial, we hypothesize that our study will have a higher rate of transplantation. [name], PhD, epidemiologist and biostatistician in the division of nephrology, will perform the statistical analyses. *Primary* efficacy (decline in cPRA $> 20\%$) and safety (discontinuation of therapy due to adverse events) endpoint will be analyzed using the exact binomial test. The *secondary* endpoint (time to transplantation) will be assessed using Kaplan-Meier analyses and log rank tests. Baseline characteristics will be compared between participants with and without the primary end point using the 2-sample t test for continuous variables and the Fisher's exact test for categorical variables. Relationships between serum BAFF/APRIL, antibodies, and baseline cPRA will be assessed using the Pearson correlation coefficient. The influence of serum BAFF/APRIL, antibodies, and bone marrow plasma cells on end points of interest will be investigated using Kaplan-Meier curves and Cox proportional-hazards models.

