3. STUDY ENDPOINTS

3.1 Primary Endpoints (safety and efficacy)

Primary efficacy and safety endpoint:

- Efficacy endpoint: A decline in cPRA > 20%.
- Safety endpoint: infections, malignancies, hematological complications including leucopenia, anemia, and thrombocytopenia, cardiovascular complications and events, distal neuropathy, gastrointestinal symptoms, and immunosuppression-related adverse effects.

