Duration of Treatment and Follow-up. All participants, those that receive a kidney transplant during the defined period and those that do not will be followed for the entire length of treatment, plus one month following the last dose of the study drug. All subjects will be asked to return for a final study visit approximately one month following the last dose of study drug. During this final study visit, subjects will undergo physical examination, bone marrow aspirate collection, CBC, LFT check, ECG and echocardiogram.

Bone Marrow Aspirate Collection Procedure: Subjects will be given the option of having the bone marrow aspirate performed under conscious sedation or local anesthetic only. The bone marrow aspirate will be collected in a transplant clinic room. If the bone marrow aspiration is done under conscious sedation, subjects will be given instructions to fast for six hours before the procedure (medications are allowed) and not to drive themselves home or operate dangerous equipment after the procedure.

Measurement of effect. We will determine the effect of ixazomib by measuring cPRA, whether patients receive a kidney transplant while participating in the study, antibody strength by MFI, and the toxicity (measured by the incidence of adverse events) of the treatment quarterly up to the end of the study.

Ixazomib Administration

All protocol-specific criteria for administration of study drug must be met and documented before drug administration. Study drug will be dispensed only to eligible patients by a member of the study team. Patients should be monitored for toxicity, as necessary, and doses of ixazomib should be modified as needed to accommodate patient tolerance to treatment; this may include symptomatic treatment, dose interruptions, and adjustments of ixazomib dose (see Section 6.3).

Capsules of ixazomib will also be referred to as study drug. Study drug will be supplied by Millennium as capsules 0.5, 2.3, and 3.0 mg ixazomib. The prescribed administration of ixazomib doses in this study is 9 mg ixazomib in a 28 day cycle. Patients should be instructed to swallow ixazomib capsules whole, with water, and not to break, chew, or open the capsules. Ixazomib should be taken on an empty stomach (no food or drink) at least 1 hour before or at least 2 hours after food. Each capsule should be swallowed separately with a sip of water. A total of approximately 8 ounces (240 mL) of water should be taken with the capsules.

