6.3 Dose-Modification Guidelines

The ixazomib dose reduction steps are 3 mg \rightarrow 2.3 mg \rightarrow 1.5 mg (Table 4-1), and the dose modification guidelines are provided in the IB and Table 4-2 and 4-3 below.

Treatment monitoring and dose modifying strategies. Liver Function Tests will be conducted twice a month for the first 3 months, then monthly thereafter. The Complete Blood Count (CBC) will be checked monthly. They will undergo clinical evaluation at baseline and every three months until the end of the study. Ixazomib dose modifying strategies will be implemented as outlined in the IB.

6.3.1 Recommended Ixazomib Criteria for Beginning or Delaying a Subsequent Treatment Cycle & Dose Modifications for Treatment Associated Toxicity

Treatment with ixazomib will use a cycle length of 28 days. For a new cycle of treatment to begin, the patient must meet the following criteria:

- ANC must be $\geq 1,000/\text{mm}^3$.
- Platelet count must be $\geq 75,000/\text{mm}^3$.
- All other nonhematologic toxicity (except for alopecia) must have resolved to \leq Grade 1 or to the patient's baseline condition

If the patient fails to meet the above-cited criteria for initiation of the next cycle of treatment, dosing should be delayed for 1 week. At the end of that time, the patient should be re-evaluated to determine whether the criteria have been met. If the patient continues to fail to meet the above-cited criteria, delay therapy and continue to re evaluate. The maximum delay before treatment should be discontinued will be 3 weeks or at the discretion of the Principal Investigator.

For dosing recommendations upon recovery, refer to Table 642 and Table 4-3.

Table 4-1 Ixazomib Dose Adjustments

| Dose Level | Dose (mg) |
|---------------|-----------|
| Starting Dose | 3.0 mg |

| | |
|-----------------------------|-------------|
| First Level Dose Reduction | 2.3 mg |
| Second Level Dose Reduction | 1.5 mg |
| Third Level Dose Reduction | Discontinue |

Once ixazomib is reduced for any toxicity, the dose may not be re-escalated.

Dosage adjustments for hematologic toxicity are outlined in Table 4-2.

Table 4-2 **Ixazomib** Dose Adjustments for Hematologic Toxicities

| Criteria | Action |
|---|--|
| Dose Modifications for Treatment Cycles | |

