| Grade 3 nonhematologic toxicity including hepatic and cardiac judged to be related to study drug If not recovered to < Grade 1 or baseline within 4 weeks | 
 Hold study drug until resolution to Grade $<$ 1 or baseline Reduce study drug 1 to next lower dose upon return to < Grade 1 or baseline | Symptomatic recommendations noted in Section 6.7 |
| Subsequent recurrence Grade 3 that does not recover to < Grade 1 or baseline within 4 weeks | 
 Hold study drug until resolution to Grade $<$ 1 or baseline Reduce study drug to next lower dose | Monitor closely, take appropriate medical precautions, and provide appropriate symptomatic care |
| Grade 4 nonhematologic toxicities including hepatic and cardiac judged to be related to study drug | 
 Consider permanently discontinuing study drug | Exceptions are cases in which the investigator determines the patient is obtaining a clinical benefit |

Once ixazomib is reduced for any toxicity, the dose may not be re-escalated.

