7.1.8 Safety Analysis

Together with the UW ICTR Data Monitoring Committee (DMC) we will develop a detailed a data and safety monitoring plan (DSMP) which will ensure ongoing safety of participating patients commensurate with the level of risk and complexity of the protocol treatment to minimize risks, integrity of trial data and scientific validity of the trial. The development of the DSMP will be guided by the NIH Policy for Data and Safety Monitoring and by the FDA Guidance on the Establishment and Operation of Clinical Trial Data Monitoring Committees. The plan will make certain that review of the conduct of research is rigorous, independent and objective, interim safety and efficacy data is collected and presented and progress towards achieving study goals is made. It will cover policies and procedures for reporting adverse events to the DSMB, IRB, and the FDA.

The safety analysis will focus on infections, malignancies, hematological complications including leucopenia, anemia, and thrombocytopenia, cardiovascular complications and events, distal neuropathy, gastrointestinal symptoms, and immunosuppression-related adverse effects. Patients will have a physical exam 5 times (beginning and end of the study, and quarterly during the study) following enrollment: Days 1, 85, 169, 253, and 373 (+ 6, - 3 for all visits except for visit 1).

- Day 1: Prior to treatment initiation. H&P, Labs, Bone Marrow Aspirate
- Day 85 + 6, - 3: Prior to treatment dose. H&P, Labs
- Day 169 + 6, - 3 Prior to treatment dose. H&P, Labs
- Day 253 + 6, - 3 Prior to treatment dose. H&P, Labs
- Day 373 + 6, - 3 After treatment completion, H&P, Labs, Bone Marrow Aspirate
- At each of these visits, the patients will undergo a medical history and physical exam, reviewing the adverse event data, vital signs, monthly labs, changes in patients' health status and medications.
- Study drug will be dispensed at each month's in-person visit, prior the initiation of the next cycle, and after reviewing the AEs and monthly labs.

Liver Function Tests (LFTs) will be conducted twice a month for the first 3 months, then monthly thereafter. The Complete Blood Count (CBC) will be checked monthly.

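### The tested safety variable, stopping treatment for adverse events, can understate toxicity because an open-label investigator may continue drug after some Grade 4 events when benefit is seen

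*Combined protocol and SAP*

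**What the plan says.** - **Tested variable.** Section 7.1: "safety (discontinuation of therapy due to adverse events) endpoint will be analyzed using the exact binomial test". No reference rate, acceptable rate or interval is given for it. The trial is open-label, has 10 patients (Section 4.2), and puts all enrolled patients in the safety analysis (Section 7.1.3).
- **Endpoint as defined elsewhere.** Section 3.1, like the Protocol Summary, gives a list: "Safety endpoint: infections, malignancies, hematological complications including leucopenia, anemia, and thrombocytopenia, cardiovascular complications and events", followed by further event types. Section 7.1.8 follows the same list: "The safety analysis will focus on infections, malignancies, hematological complications including leucopenia, anemia, and thrombocytopenia". Section 6.2 refers to "toxicity (measured by the incidence of adverse events) of the treatment quarterly up to the end of the study". None of these names stopping treatment as the endpoint.
- **Benefit exception.** For Grade 4 non-hematologic toxicity related to study drug, Table 4-3 asks only that permanent stopping be considered, and adds: "Exceptions are cases in which the investigator determines the patient is obtaining a clinical benefit". Clinical benefit is not defined. The separate row for Grade 4 peripheral neuropathy calls for stopping and has no exception.
- **Delay limit.** Section 6.3.1: "The maximum delay before treatment should be discontinued will be 3 weeks or at the discretion of the Principal Investigator". Table 4-2, for hematologic toxicity, repeats this.
- **Compliance.** Section 6.10, on a second shortfall: "If they fall below 75% study drug compliance again, they will be withdrawn". Section 6.12 lists "Non-compliance as defined above in section 6.10" separately from stopping for an adverse event, and asks for one primary reason for withdrawal.

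**The concern.** A patient enters the tested count only if someone decides to stop the drug and records an adverse event as the reason. Two patients with the same Grade 4 event can be scored differently because one is thought to be benefiting. The protocol does not define benefit. In a desensitization trial a falling cPRA is a natural reading, although that is an inference. cPRA is measured every three months, and no blinding of the investigator to it is described.

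The safety proportion is then not independent of the efficacy proportion reported beside it. At stake is the one safety figure that carries a formal analysis. It could look favourable partly because patients who seemed to respond were kept on drug.

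**Working it through.** **1. The plan's own figures.** The only numerical examples, in Section 7.1.1, concern efficacy. The exact (Clopper-Pearson) 95% CI for 3/10 is 6.7% to 65.2%, as stated. The chance of at least one success in 10 at a true rate of 0.2 is 1 − 0.8^10 = 0.893, which agrees with the stated value above 80%. There is no safety figure to reproduce.

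**2. Which rules leave the count to discretion.**

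| Situation | Protocol action | Can the patient go uncounted? |
|---|---|---|
| Grade 4 related non-hematologic toxicity (Table 4-3) | Consider stopping; exception for benefit | Yes, and the reason is tied to perceived benefit |
| Grade 4 peripheral neuropathy (Table 4-3) | Stop | Not under the text |
| Toxicity delay beyond 3 weeks (Section 6.3.1, Table 4-2) | Stop, or investigator discretion | Yes, but the text gives no link to benefit |

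**3. Size per patient.** With n = 10, one patient is 1/10 = 10 points. Exact 95% CIs:

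- 0/10: 0% to 30.8% (upper limit 1 − 0.025^(1/10))
- 1/10: 0.3% to 44.5%
- 2/10: 2.5% to 55.6%
- 3/10: 6.7% to 65.2%

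**4. Effect of incomplete counting.** Let p be the true rate of toxicity that would otherwise lead to stopping, and s the share that is counted. The documents give neither, so both are assumptions. Expected count = 10·p·s; chance that none is counted = (1 − p·s)^10.

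| p | s = 1 | s = 0.75 | s = 0.5 |
|---|---|---|---|
| 20% | 2.0; 10.7% | 1.5; 19.7% | 1.0; 34.9% |
| 30% | 3.0; 2.8% | 2.25; 7.8% | 1.5; 19.7% |
| 40% | 4.0; 0.6% | 3.0; 2.8% | 2.0; 10.7% |

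**5. Loss in responders only.** Assume 3 responders, a 30% rate in everyone, and half of the responders' events uncounted. The expected count is 3 × 0.3 × 0.5 + 7 × 0.3 = 0.45 + 2.10 = 2.55, against 3.0. The loss is less than half a patient.

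**6. The compliance route.** Twelve cycles of 3 doses give 36 doses, or 9 in a three-cycle quarter. Missing 2 gives 7/9 = 77.8%; missing 3 gives 6/9 = 66.7%, below 75%. Withdrawal needs this to happen twice. The calculation assumes that compliance is doses taken over doses planned in the quarter, but Section 6.10 states no denominator.

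**The case against.** The strongest reply is that stopping treatment is not the whole safety analysis. Sections 3.1 and 7.1.8 rest on event types. Section 8.1.2 names Grade 4 neuropathy, cardiac and hepatic toxicity as examples of medically important serious events. Section 8.2 requires serious events to be reported whatever their cause, and Section 9.1 has the data monitoring committee review their number and seriousness. A patient kept on drug after a Grade 4 event is still visible there. This stands. A reader might infer that toxicity as a whole is undercounted, and the documents do not support that.

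The reply does not repair the tested rate. The event record also has loose ends: Section 9.1 says in one place that only related adverse events are entered in the database and in another that all are.

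Three further points also stand:

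- The benefit exception does not reach every Grade 4 event. Peripheral neuropathy, one of the three toxicities named in the primary objective, is outside it.
- Discretion over the delay limit is not tied to benefit, and the wording does not say that it can only lengthen the delay.
- The first scheduled on-treatment cPRA is at Day 85, so early decisions would normally be made without one.

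A reader might also infer that toxicity-driven missed doses will be relabelled as non-compliance. The plan does not provide for this. It is possible only because the plan does not say how held or skipped doses enter compliance or how such a withdrawal is attributed. Doses held under Section 6.3 may well not count as missed, and Section 6.12 allows an adverse event to be recorded as the primary reason. Nothing links this route to response.

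**Conclusion.** The concern holds in a limited form. The discontinuation rate tested in Section 7.1 can understate toxicity, because it depends on open-label decisions that Table 4-3 partly ties to perceived benefit. Any bias from that exception would run towards fewer counted patients among those thought to be responding. This is a risk created by the rules and not a demonstrated effect.

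Its size is unknown. Each uncounted patient costs 10 points. The contrast of 2/10 with 0/10 supposes two retained patients and is not a forecast; under the assumptions in step 5 of the working the expected loss confined to responders is 0.45 of a patient. No decision threshold is attached to the safety variable, so no stated conclusion would reverse. What is exposed is how the formally analysed safety figure reads. The mismatch between Section 7.1 and Sections 3.1 and 7.1.8 adds to this, because the plan does not settle which measure is primary. No view is taken on which treatment-stopping rule is right.

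**What to change.** Leave clinical discretion unchanged, and add to the analysis.

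1. In Section 7.1, keep the discretionary discontinuation rate. Beside it, report the proportion of patients, with an exact 95% CI, who either stopped ixazomib for an adverse event or met a discontinuation criterion stated in the protocol, whether or not drug was continued. The criteria are Grade 4 related non-hematologic toxicity, Grade 4 peripheral neuropathy, and a toxicity delay beyond 3 weeks. Grading and relatedness remain investigator assessments, but the decision to continue no longer affects this count.
2. Reconcile Section 7.1 with the Protocol Summary and Sections 3.1 and 7.1.8, so that one primary safety endpoint is stated. Reconcile also the two statements in Section 9.1 on which adverse events are entered.
3. As a secondary clarification, record the reason for each missed dose while treatment is under way. In a sensitivity count, include withdrawals for non-compliance that follow doses missed because of an adverse event.

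The cost is analysis-plan wording, one case report form field, a little more analysis, and a safety figure that may look less favourable.
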